Tertiary/exploratory	
 To evaluate the impact of Soliqua 100/33 on additional measures of glycemic control and variability in participants with T2DM 	
 Change (mg/dL) from baseline to week 16 in mean of daily difference (MODD) Change (%) from baseline to week 16 in TAR (>250 mg/dL) Change (%) from baseline to week 16 in time below range (TBR); <70 mg/dL) Correlation of change in the percentage of TIR (70-180 mg/dL) and change in patient reported outcome (PRO) from baseline to week 16 Correlation of percentage of TIR (70-180 mg/dL) and HbA1c percentage achieved at week 16 Association of participants reaching 60 units/day insulin glargine U100 and TIR >70% Change in HbA1c percentage from baseline to week 16 Change in the percentage from baseline to week 16 for Time in Tight Range (TITR)(70-140 mg/dL) Proportion of participants with TIR (70–180 mg/dL) > 70% of each day at week 16 Proportion of participants with ≥5% absolute improvement from baseline to week 16 in TIR (70–180 mg/dL) Proportion of participants with ≥10% absolute improvement from baseline to week 16 in TIR (70–180 mg/dL) Proportion of participants with improvement in HbA1c >0.5% points from baseline to week 16 without an increase in TBR (<54 mg/dL) of >0.5% Proportion of participants with ≥10% absolute improvement from baseline to week 16 in TIR (70–180 mg/dL) without an increase in TBR (<54 mg/dL) of >0.5% Proportion of participants with TIR (70–180 mg/dL) > 70% per day and TBR (<70 mg/dL) < 4% per day at week 16

Objectives	Endpoints

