2 SAMPLE SIZE DETERMINATION

In LPS16990, a total of 100 participants will be enrolled in the study. Sufficient participants will be screened from 20 sites to include 100 participants, such that approximately 82 evaluable participants complete the study (anticipating that approximately 15% of participants discontinue the study before Week 16).

The sample size is based on the primary objective to demonstrate the significant mean change (increase) in the percentage of TIR (70-180 mg/dL) from baseline to week 16 with sufficient power. A total sample size of 82 evaluable participants has 95% power to detect an absolute increase in TIR means of 10%, assuming a standard deviation (SD) of 25 for the change in TIR, with a two-sided type I error of 0.05. Anticipating a 15% loss to follow-up rate, 100 participants would need to be enrolled.

Assumptions for Sample Size Determinations

- Participants with an HbA1c $\geq 9\%$ are in range 40% of the time or less (Batellino et al 2019).
- Per Vigersky and McMahon, every 10% increase in TIR corresponds to 0.8% HbA1c reduction (Vigersky and McMahon 2019).
- Post hoc analyses from the LixiLan-O study in participants with an HbA1c of $\geq 9\%$ produced an HbA1c reduction of 2.9% at 30 weeks (Davies et al 2019). Therefore, 0.8% HbA1c reduction (considered equal to 16% improvement in TIR) at week 16 seems reasonable.
- Assumption for SD is 25. In the AWARD-4 study in participants with T2DM, the increase in TIR at Week 26 was 20% to 30%, and the SE was approximately 3.0 (corresponding to an SD of approximately 20)

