- Correlation of percentage of TIR [70 – 180 mg/dL] and HbA1c percentage achieved at week 16. The correlation of percentage of TIR and HbA1c achieved at week 16 will estimate the relationship between the two variables.
- Association of participants reaching 60 units/day insulin glargine U100 and TIR > 70%.
- Change in HbA1c percentage from baseline (run-in) to week 16. The alternative hypothesis to be tested is that the HbA1c will decrease from baseline to week 16. A two-sided 95% CI will be presented. This analysis will be based on participants in the enrolled set who have non-missing outcomes at baseline and week 16.
- Change in the percentage from baseline (run-in) to week 16 for TITR (70-140 mg/dL). The end point will determine the percentage of time spent in the glycemic tight target range. This is calculated as 100 times the number of recorded measurements in the glycemic target range, (70-140 mg/dL) inclusive, divided by the total number of recorded measurements per time block and comparing week 16 to baseline over a 14-day period to determine change. A two-sided 95% CI will be presented.
- Proportion (%) of participants with TIR (70–180 mg/dL) > 70% each day at week 16. To calculate the proportion of participants achieving TIR of >70% each day, a sum of the number of participants with more than 67 15-minute intervals with glucose values in range per day for all compliant days divided by the total number of participants. The endpoint will be calculated using all CGM glucose readings available throughout each day for two weeks at the end of study. As this is a binary outcome the endpoint will be summarized with proportions and 95% CI using the Clopper Pearson exact method. A two-sided 95% CI will be presented.
- Proportion (%) of participants with $\geq 5\%$ absolute improvement from baseline in TIR (70-180 mg/dL). Absolute improvement is defined as an increase in TIR from baseline to week 16. To calculate the proportion of participants achieving $\geq 5\%$ in TIR absolute improvement from baseline a sum of the number of participants with a positive percent change $\geq 5\%$ will be divided by the total number of participants. The endpoint will be calculated using all CGM glucose readings available throughout each day for each two-

week time blocks. As this is a binary outcome the endpoint will be summarized with proportions and 95% CI using the Clopper Pearson exact method. A two-sided 95% CI will be presented.

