- Proportion (%) of participants with $\geq 10\%$ absolute improvement from baseline in TIR (70-180 mg/dL). Absolute improvement is defined as an increase in TIR from baseline to week 16. To calculate the proportion of participants achieving $\geq 10\%$ absolute improvement in TIR from baseline a sum of the number of participants with a positive percent change $\geq 10\%$ are divided by the total number of participants. The endpoint will be calculated using all CGM glucose readings available throughout each day for each two-week time blocks. As this is a binary outcome the endpoint will be summarized with proportions and 95% CI using the Clopper Pearson exact method. A two-sided 95% CI will be presented.
- Proportion (%) of participants with improvement in HbA1c $>0.5\%$ points without an increase in TBR (<54 mg/dL) of $>0.5\%$. Improvement is defined as an increase in HbA1c from baseline to week 16. To calculate the proportion of participants achieving $>0.5\%$ improvement of HbA1c from baseline and with $< 0.5\%$ change in TBR participants will be summed then divided by the total number of participants. The endpoint will be summarized based upon CGM data reporting both percentages and 95% CI using the Clopper Pearson exact method. A two-sided 95% CI will be presented.
- Proportion of participants with $\geq 10\%$ absolute improvement from baseline in TIR (70-180 mg/dL) without an increase in TBR (<54 mg/dL) of $>0.5\%$. Absolute improvement is defined as an increase in TIR from baseline to week 16. A sum of participants with both $\geq 10\%$ of improvement from baseline in TIR and no increase in TBR of more than 0.5% will be divided by the total number of participants. The endpoint will be summarized based upon CGM data reporting both percentages and 95% CI using the Clopper Pearson exact method. A two-sided 95% CI will be presented.
- Proportion of participants with TIR (70–180 mg/dL) $>70\%$ and TBR (<70 mg/dL) $<4\%$ at Week 16. To calculate the proportion of participants achieving TIR $>70\%$ and TBR $<4\%$, a sum of the number of participants with both TIR $>70\%$ and TBR $<4\%$ divided by the total number of participants. The endpoint will be summarized based upon CGM data reporting both percentages and 95% CI using the Clopper Pearson exact method. A two-sided 95% CI will be presented.

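### SAP 4.5.1 reverses the HbA1c responder rule and states two TIR responder rules on contradictory scales

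*SAP*

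**What the plan says.** The protocol's endpoint list does not contain these responder endpoints, so the SAP is their only definition.

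**HbA1c composite.** SAP 4.5.1 titles it as an HbA1c improvement of more than 0.5 points without a rise of more than 0.5% in time below 54 mg/dL. It then adds: "Improvement is defined as an increase in HbA1c from baseline to week 16". In the same section, the endpoint for mean change in HbA1c has a decrease as its alternative hypothesis.

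**Stand-alone TIR responders.** SAP Table 2 lists participants with ≥5% and ≥10% "absolute improvement from baseline to week 16 in TIR". Section 4.5.1 explains the term this way: "Absolute improvement is defined as an increase in TIR from baseline to week 16". That gives a direction but no scale. The counting sentence for the ≥10% endpoint then puts both terms together: "absolute improvement in TIR from baseline a sum of the number of participants with a positive percent change" of at least 10%. The ≥5% endpoint is counted the same way, as "a sum of the number of participants with a positive percent change" of at least 5%.

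**TIR composite.** The endpoint combining a ≥10% TIR gain with no meaningful rise in time below range is worded differently. It counts participants with at least 10% "of improvement from baseline in TIR and no increase in TBR of more than 0.5% will be divided by the total number of participants". It does not mention percent change, and it does not state a scale either.

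**The concern.** The HbA1c line sets the direction of the endpoint. A programmer who codes it as written will classify a rise in HbA1c as success.

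The TIR rule matters because the variable is already a percentage. A 10% improvement can mean 10 percentage points or one tenth of the baseline value, and the SAP expects baseline values to be low. Percent change ordinarily means change relative to baseline. On that reading, participants gaining only a few points are counted under a title that promises an absolute gain of 5 or 10. The stand-alone ≥10% endpoint and its composite could also be programmed on different scales and would then not be comparable.

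**Working it through.** **HbA1c direction.** Let D be Week 16 HbA1c minus baseline HbA1c. The rule as written counts D > +0.5; the title needs D < −0.5. Take the 0.8-point reduction that SAP section 2 uses in planning: D = −0.8. The title counts this participant (subject to the time-below-range condition), and the written rule does not. A participant with D = +0.8 is handled the opposite way. No assumption about scale is needed.

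**TIR: inputs.**
- Baseline TIR: SAP section 2 says only that such participants "are in range 40% of the time or less". The 20% lower end used below is an assumption.
- Change in TIR: mean 10 points, SD 25 (SAP section 2).

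The documents give no figure for the responder rates. The planning inputs do reproduce the stated sample size: (25 × (1.960 + 1.645) / 10)² = 81.2, rounded up to 82. Exact t-test power at 82 is 94.7%, in line with the stated 95%.

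**TIR: cut-offs.** Read in points, the cut-offs are 5 and 10 at every baseline. Read as relative, a participant with baseline B responds when the gain is at least 0.05 × B or 0.10 × B. Both are below 5 and 10 whenever B is under 100, so the relative reading can only add responders. At B = 0 it is undefined.

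**TIR: illustrative rates.** P(change ≥ c) = Φ((10 − c)/25), with change independent of baseline.

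In points: Φ(0.20) = 57.9% for ≥5, and Φ(0) = 50.0% for ≥10.

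Relative reading (excess taken from unrounded values):

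| Baseline TIR | Cut-off, ≥5% | Responders | Excess | Cut-off, ≥10% | Responders | Excess |
|---|---|---|---|---|---|---|
| 20% | 1.0 point | Φ(0.36) = 64.1% | 6.1 | 2.0 points | Φ(0.32) = 62.6% | 12.6 |
| 30% | 1.5 points | Φ(0.34) = 63.3% | 5.4 | 3.0 points | Φ(0.28) = 61.0% | 11.0 |
| 40% | 2.0 points | Φ(0.32) = 62.6% | 4.6 | 4.0 points | Φ(0.24) = 59.5% | 9.5 |

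**Sensitivity.** Other planning values in the SAP give mean changes of 16 and 20 and an SD of about 20. Across the combinations tried (10/25, 16/25, 10/20, 16/20, 20/20), at baselines of 20% to 40%, the excess is about 4 to 8 points for ≥5% and 9 to 16 points for ≥10%.

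**The case against.** A reader might infer that the TIR responder rates will be inflated. The documents do not support that. The word absolute appears in Table 2, in the 4.5.1 titles and in the counting sentences themselves. For range metrics the SAP also uses percent wording for plain differences. Table 3 labels the TAR endpoint a mean percent change, yet 4.4.1.1 calculates TAR at both times and reports the change. Section 4.5.1 labels TAR above 250 mg/dL and TBR as change (%) and reports a difference. The primary TIR endpoint is itself a difference, and 4.3.2 describes its mean change as being in percentage. CV is the one endpoint described as a percent change with that percent change reported, but no formula divides the change by baseline, so it does not settle the matter. This objection stands: the TIR rule contradicts itself, but it is not shown to be relative.

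A reader might also extend the point to all three TIR-improvement endpoints. Only two carry the percent-change wording; the composite is merely silent on scale.

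The rates are also rough. Normal(10, 25) applied at a baseline of 20% puts Φ(−30/25) = 11.5% of participants below zero TIR at Week 16, and at 30% it puts Φ(−40/25) = 5.5% there. They indicate order of size and are not predictions.

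On HbA1c, a programmer may well notice the slip, because the same section expects a decrease. That lowers the practical risk, but the written rule is still wrong.

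**Conclusion.** Two wording errors stand. The HbA1c rule is reversed as written, whatever is assumed about scale. The two stand-alone TIR responder rules name one scale and count on what is ordinarily another, and no formula resolves it.

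The size of the TIR effect is conditional. It is nil if the rule is read as points. If it is read as relative, the excess is roughly 5 to 6 percentage points of responders at ≥5% and 9 to 13 at ≥10%, given a 20% to 40% baseline and a normal change independent of baseline.

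All of these endpoints are exploratory, lie outside the testing hierarchy and are summarised as proportions with exact intervals. The sample size, the primary analysis and the key secondary analyses do not depend on them.

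**What to change.** In SAP 4.5.1:

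- Define HbA1c improvement as a decrease from baseline to Week 16 of more than 0.5 percentage points.
- Define TIR response as Week 16 TIR minus baseline TIR of at least 5 (or at least 10) percentage points, and delete percent change from both counting sentences.
- State the same percentage-point scale in the composite of a ≥10% TIR gain without a rise in time below range.
- Add percentage points to the matching lines of Table 2.

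Make the change before database lock and check the programming specification against it. The cost is SAP wording and a version entry. It needs no new data, no change in sample size and no change to the protocol's endpoints.

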3 ANALYSIS SETS

The following analysis sets for analyses are defined:

Table 4 - Analysis Sets

Analysis Set	Description
Screened	All participants who signed the ICF.
Enrolled	All eligible participants who are dispensed Soliqua 100/33 and sign the ICF.
Efficacy analysis set	All enrolled participants who receive ≥ 1 dose of Soliqua 100/33 and have compliant ^a CGM data at baseline.
Safety set	All enrolled participants who receive ≥ 1 dose of Soliqua 100/33.

- a. CGM compliance is defined as 1) at least 8 out of 14 days (not necessarily consecutive) have 100% of evaluable CGM data per 24-hour period (at least 8 days with 96 records minimum per day) OR 2) at least 9 out of 14 days (not necessarily consecutive) have $\geq 89\%$ of evaluable CGM data per 24-hour period (at least 9 days with 85 records minimum per day) OR 3) at least 10 out of 14 days (not necessarily consecutive) have at least $\geq 80\%$ of evaluable CGM data per 24 hour period (at least 10 days with 77 records minimum per day)

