4.3 PRIMARY ENDPOINT(S) ANALYSIS

4.3.1 Definition of endpoint(s)

The primary endpoint is the difference from baseline to week 16 in the percentage of TIR of 70-180 mg/dL using 14 days of CGM data at baseline. The percentage of time spent in the glycemic target range will be calculated as 100 times the number of recorded measurements in the glycemic target range, (70-180 mg/dL) inclusive, divided by the total number of recorded measurements. All the efficacy assessments collected during the study will be used, including those obtained after IMP discontinuation or introduction of rescue therapy. Regardless of intercurrent events at week 16, the value for the mean change in the percentage of TIR will be used.

CGM data

CGM compliance is defined as:

1. at least 8 out of 14 days (not necessarily consecutive) have 100% of evaluable CGM data per 24-hour period (total of 768 records on 8 days) OR
2. at least 9 out of 14 days (not necessarily consecutive) have $\geq 89\%$ of evaluable CGM data per 24-hour period (total of 768 records on 9 days and at least 9 days with 85 records minimum) OR
3. at least 10 out of 14 days (not necessarily consecutive) have at least $\geq 80\%$ of evaluable CGM data per 24-hour period (total of 768 records on 10 days and at least 10 days with 77 records minimum)

during baseline (the run-in period) as well as week 16.

During the run-in period or end of treatment period, CGM device reinsertion will be allowed for participants who do not meet the compliance criteria over a 14-day period as a result of premature sensor failure.

Baseline will be defined as the first 14 evaluable days of evaluable CGM data prior to first day of treatment and referred to as the run-in period in the graphical study design. An evaluable day is defined as a 24-hour period with $\geq 80\%$ non-missing measurements. Only evaluable days will be included in the analysis. Week 16 will be defined as the first 14 evaluable days of evaluable CGM data starting at day 95 or later.

The first day of CGM data will start at time of device insertion and subsequent days will start every 24 hours. If the device is re-inserted, device with the most compliant data will be used and if neither session is evaluable, the combined data from both sessions will be used as evaluable data. For subsequent reinsertions, the day will start at time of reinsertion.

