Unless otherwise specified, outcome variables based on CGM data will use subjects in the efficacy analysis set with compliant data at baseline.

Percent time in the glucose range is defined as the total number of 15-minute increments where a participant's blood glucose falls within range of ≥ 70 to ≤ 180 mg/dL (≥ 3.9 to ≤ 10 mmol/L) divided by the total number of observed 15-minute increments in that period. Percent time in range will be calculated for baseline (run-in) and for week 16.

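### Two exploratory responder rules in SAP 4.5.1 are wrong as written: HbA1c improvement is defined as a rise, and daily TIR >70% is a fixed count that is right only for a complete 96-reading day

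*SAP*

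**What the plan says.** **HbA1c/TBR composite.** SAP Table 2 labels the endpoint "Proportion of participants with improvement in HbA1c >0.5% points from baseline to week 16 without an increase in TBR" (<54 mg/dL) of more than 0.5%. The derivation in SAP 4.5.1 then says "Improvement is defined as an increase in HbA1c from baseline to week 16", and counts participants whose TBR change is below 0.5%. For the separate HbA1c change endpoint, the same section says "The alternative hypothesis to be tested is that the HbA1c will decrease from baseline to week 16".

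**Daily TIR >70%.** SAP 4.5.1 counts participants "with more than 67 15-minute intervals with glucose values in range per day for all compliant days". CGM compliance in SAP section 3 can be met by "at least 10 days with 77 records minimum per day". SAP 4.3.1 repeats this as "total of 768 records on 10 days and at least 10 days with 77 records minimum", and defines an evaluable day as one with at least 80% of measurements present. The same section defines percent TIR as in-range increments "divided by the total number of observed 15-minute increments in that period".

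**Absolute TIR gains of at least 5% and 10%.** Both are labelled absolute, but SAP 4.5.1 counts them as "a sum of the number of participants with a positive percent change" at or above the cut-off.

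**DM-SAT.** SAP 4.5.2 divides the lifestyle and convenience sums by 50 and the total by 160. A scale is set to missing only when more than 25% of its items are missing. The SAP does not say how a scale with fewer missing items is scored.

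**The concern.** The composite and the TIR responder endpoints appear in the SAP but not among the protocol's endpoints, so SAP 4.5.1 is their only derivation and no protocol rule corrects it. A programmer who follows the HbA1c sentence reports a reversed limb. One who quietly corrects it departs from an approved SAP without a record.

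The count of 67 is harder to notice, because it is correct for a full day. On any shorter day it demands more than 70%. The responder rate then depends on sensor completeness as well as on glucose. Since every compliant day must pass, one short day can turn a responder into a non-responder.

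**Working it through.** **1. HbA1c direction.** Inputs: mean change -0.8 points (the reduction called reasonable in SAP section 2); SD 1.0 to 1.5 (assumed, not in the documents); normal distribution.

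- Intended limb, P(change < -0.5) = Φ((-0.5 + 0.8)/SD): Φ(0.30) = 0.618 at SD 1.0; Φ(0.20) = 0.579 at SD 1.5.
- Written limb, P(change > +0.5) = 1 - Φ((0.5 + 0.8)/SD): 0.097 at SD 1.0; 0.193 at SD 1.5.
- Single cases: 10.0 to 9.4 is a responder as intended but not as written. 10.0 to 10.6 is the reverse.
- If the mean change were -2.9, the 30-week figure also cited in SAP section 2, about 95-99% would meet the intended limb and about 0-1% the written one.

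On the TBR limb, a change below 0.5% and no increase above 0.5% differ only at exactly 0.5% if change is signed. If change is unsigned, a participant whose TBR falls by 0.5 points or more would also fail.

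**2. Daily TIR >70%.** A full day has 24 × 60 / 15 = 96 readings, and 0.70 × 96 = 67.2. So 67/96 = 69.8% fails and 68/96 = 70.8% passes: the SAP's count is reproduced for a complete day. The shortest evaluable day has 77 readings, since 0.80 × 96 = 76.8. For a day with n recorded readings:

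| n | Smallest count above 0.70n | What 68 readings means |
|---|---|---|
| 96 | 68 | 70.8% |
| 95 | 67 | 71.6% |
| 90 | 64 | 75.6% |
| 85 | 60 | 80.0% |
| 77 | 54 | 88.3% |

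For n from 77 to 96, the two rules agree only at n = 96. On a 77-reading day, counts of 54 to 67 (70.1% to 87.0%) exceed 70% but fail the fixed count. The fixed count never passes a day that is at or below 70%. A participant in range for 75% of readings every day passes only if each day has at least 68/0.75, rounded up to 91 readings. At 80% the figure is 68/0.80 = 85.

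**3. Absolute or relative TIR gain.** Illustration: change distributed N(10, 25), as in the sample-size assumptions, with baseline TIR 40%. A relative gain of 10% is then 4 points and of 5% is 2 points.

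- P(change ≥ 10) = 50.0%, against P(change ≥ 4) = 59.5%.
- P(change ≥ 5) = 57.9%, against P(change ≥ 2) = 62.6%.

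SAP section 2 puts baseline TIR at 40% or less. A lower baseline widens the gap.

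**4. DM-SAT.** Suppose every answered item scores 7, so the complete score is 0.70. Summing answered items over the full denominator gives 4 × 7/50 = 0.56 with 1 of 5 missing, 15 × 7/160 = 0.66 with 1 of 16 missing, and 12 × 7/160 = 0.53 with 4 of 16 missing. The 3-item scales are unaffected: one missing item is 33%, above the 25% limit.

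**The case against.** **HbA1c.** The wrong sign looks like a slip carried over from the neighbouring TIR bullets, and the context shows what was meant. That is fair as to intent. The sentence is nevertheless the operative definition, and it contradicts its own section. The size of the reversal depends on the assumed mean and SD; its existence does not.

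**Daily TIR.** This is the strongest objection. The Table 2 label speaks of more than 70% of each day, which could mean 70% of the full 24 hours, making 67 exact. But nothing in the SAP counts missing readings as out of range, SAP 4.3.1 uses observed readings as the denominator, and the bullet itself says it uses the readings available. If a 24-hour denominator was intended, it must be stated.

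It is also true that a compliant day is not a defined term, because compliance is a participant-level rule. The defined term is the evaluable day, and SAP 4.3.1 admits only evaluable days to the analysis. A participant who qualifies through eight complete days can still contribute further evaluable days with fewer than 96 readings, so that route does not remove the problem.

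**What stands.** The documents give no expected sensor completeness, so the number of participants misclassified cannot be estimated. With baseline TIR at 40% or less and a planned gain of 10 points, few may exceed 70% on every day under either rule. For the absolute TIR responders, percentage points are probably meant. The DM-SAT figures rest on one unfavourable reading that the SAP does not state, and the instrument's own scoring instructions are not available here.

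**Conclusion.** The concern holds. The HbA1c definition is reversed, and the fixed count departs from >70% on every evaluable day with fewer than 96 readings, always towards fewer responders. Both conclusions follow from the SAP text and simple arithmetic. Only the 58-62% against 10-19% comparison needs an assumed SD and normality, with the mean taken from the plan.

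The TIR-gain and DM-SAT points are matters of wording. They change results only if TIR gain is programmed as relative change, or if incomplete questionnaires are summed over the full denominator.

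The reach is limited to exploratory and patient-reported endpoints, and the affected responder proportions are reported with exact confidence intervals and no test. The corrections should be made, but nothing confirmatory depends on them.

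**What to change.** Make four one-line edits to the SAP before database lock:

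1. **HbA1c/TBR composite:** improvement is a decrease in HbA1c of more than 0.5 percentage points, with TBR <54 mg/dL not increased by more than 0.5 percentage points.
2. **Daily TIR:** in-range readings divided by recorded readings that day exceed 70% on every evaluable day, as SAP 4.3.1 defines that term.
3. **TIR gain responders:** replace the percent-change wording with Week 16 TIR minus baseline TIR, in percentage points.
4. **DM-SAT lifestyle, convenience and total (SAP 4.5.2):** when no more than 25% of items are missing, the score is the sum of answered items divided by 10 times the number answered. Check this first against the instrument's scoring instructions.

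No new data are needed. Edit 2 leaves the daily-TIR responder percentage the same or higher. Edit 3 lowers the TIR-gain percentages only if relative change had been programmed. The documents do not show whether lock has taken place; if it has, the same text belongs in a dated clarification.
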